## Plan of investigation

The study design of this study is a prospective observational cohort study. We will use a snapshot study design, to include a large cohort of patients with a clinical suspicion of ASBO over a period of 6 months. This design has previously been used in the Dutch surgical society to gather data of a large group of patients over a short period of time (10). We will include as many patients as possible with a clinical suspicion of ASBO over a period of 6 months. We will contact every hospital in our country with an informative letter about our research. When the hospital accepts to participate in the collaborative study group, a digital snapshot questionnaire will be sent to provide hospital characteristics and patient data about symptoms, diagnosis, imaging, risk factors and treatment. The questionnaires will be filled by local collaborating research partners, for each patient with a suspicion of ASBO. The questions will be clear and easy to fill in. Therefore it is not a big threshold for the hospitals to participate and a lot of information can be received.

The database will be finished in Castor, in which the questionnaires will be filled in. We aim to include 500 patients with ASBO over 6 months of time. Our analysis will include regression analysis for variation in clinical management and outcome of ASBO treatment. The results will be used to form new hypotheses and update guidelines on management of ASBO.

The METC of the Radboudumc has given approval for this study. This study is not WMO- compulsory.

## Data and statistical analysis

Baseline data consisted of patients age, sex, Charlson comorbidity index, ASA classification and the number of previous abdominal operations. Categorical data will be analysed using a Chi-square or Fisher's exact test, as appropriate. Continuous data will be analysed using independent t-test or Mann-Whitney U test if not normal distributed. Continuous variables are presented as means with standard deviation, or medians with interquartile range (25–75) if non-normal distribution. Dichotomous or categorical variables are presented as absolute numbers and percentages.  $P < 0.05$  was considered significant. All analyses will be performed using SPSS version 23.0 (Armonk, NY: IBM Corp).

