## Purpose and Research Question

In this research the differences in the management and outcomes will be studied from patients admitted with ASBO to surgical emergencies units in the Netherlands. The research question is:

*"What is the impact of different variations in management and treatment of adhesive small bowel obstruction in the Netherlands on patient outcomes?"*

A nationwide cohort is being observed over a short period of time, to answer the following four defined questions.

1. How many patients in the Netherlands presenting with adhesive small bowel obstruction have a CT-scan in their diagnostic work-up? And in how many patients does CT-scan impact initial management of ASBO (i.e. different cause of SBO found, or conservative trial vs. direct surgery)?
2. How long do Dutch surgeons continue a conservative trial in patients with persistent obstruction who are not clinically deteriorating?

3. Does continuing a conservative trial for more than 72 hours adverse impact final outcomes?
4. How many patients that are surgically treated for ASBO in the Netherlands have laparoscopic surgery and what are the outcomes of laparoscopic surgery?

The analysis of these defined questions will offer insights in how differences in management can impact outcome. Further, the data will also be used to generate new hypotheses on best practice in management of ASBO.

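### The named tests assume independent patients and the announced regression has no stated model or hospital term, although patients are nested in hospitals and the effect of management variation on outcome is the main question

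*Combined protocol and SAP*

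**What the plan says.** The section Data and statistical analysis names four tests. For continuous data, "Continuous data will be analysed using independent t-test or Mann-Whitney U test if not normal distributed". For categorical data, "Categorical data will be analysed using a Chi-square or Fisher's exact test, as appropriate". Significance is P < 0.05, with sidedness not given. Categorical results are presented as numbers and percentages, and no confidence interval is mentioned.

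Regression appears once, under Plan of investigation: "Our analysis will include regression analysis for variation in clinical management and outcome of ASBO treatment". No model type, outcome, covariate list, hospital term or variance method follows, there or elsewhere.

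The same section makes the study multicentre: "We will contact every hospital in our country with an informative letter about our research". Each hospital that joins receives a form: "a digital snapshot questionnaire will be sent to provide hospital characteristics and patient data". No use of the hospital characteristics in the analysis is described. On the purpose, it says: "The results will be used to form new hypotheses and update guidelines on management of ASBO".

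Under Purpose and Research Question, the overall question is the impact of management variation on patient outcomes. Question 3 is an effect question: "Does continuing a conservative trial for more than 72 hours adverse impact final outcomes". Question 4 is partly a count: "How many patients that are surgically treated for ASBO in the Netherlands have laparoscopic surgery and what are the outcomes of laparoscopic surgery".

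**The concern.** Patients treated in one hospital share surgeons, protocols, case mix and local outcome levels. When both the management choice and the outcome vary between hospitals, two things can go wrong in a pooled comparison.

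- **Variance.** The standard error from a t-test or chi-square test is too small, so P values are too small.
- **Confounding.** If hospitals that favour one approach also have better or worse outcomes for other reasons, the comparison mixes the effect of management with differences between hospitals.

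This study sets out to learn from variation in practice, so hospital is close to the centre of the question. Much of the plan is descriptive and hypothesis-generating, but it also tests at P < 0.05, asks whether a longer conservative trial harms outcome, and intends to inform guidelines. An anti-conservative or confounded comparison could therefore carry weight.

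**Working it through.** The plan has no figure of its own to reproduce here: the target of 500 comes without power, effect size, number of hospitals or ICC.

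**Inputs from the documents**
- n = 500 patients with ASBO (Plan of investigation).
- 20-30% of cases need operation (Background). Applied to 500: 0.20 × 500 = 100 to 0.30 × 500 = 150 operated patients, relevant to question 4.
- Alpha 0.05 (Data and statistical analysis), taken as two-sided.

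**Assumed inputs**
- H = 20-60 hospitals of equal size.
- Exposure ICC 0.2-0.4 and outcome ICC 0.05-0.10.

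**Step 1: error of a test that ignores hospital.** With m = n/H, the design effect is DE = 1 + (m − 1) × ICCx × ICCy, and the actual error is 2 × (1 − Φ(1.96/√DE)).

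| Patients | H | ICCx / ICCy | m | DE | Actual error |
|---|---|---|---|---|---|
| 100 | 60 | 0.2 / 0.05 | 1.67 | 1.007 | 5.1% |
| 125 | 40 | 0.3 / 0.075 | 3.13 | 1.048 | 5.6% |
| 150 | 20 | 0.4 / 0.10 | 7.5 | 1.26 | 8.1% |
| 500 | 60 | 0.2 / 0.05 | 8.33 | 1.073 | 5.9% |
| 500 | 40 | 0.3 / 0.075 | 12.5 | 1.259 | 8.1% |
| 500 | 20 | 0.4 / 0.10 | 25 | 1.96 | 16.2% |

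With weak clustering (0.1 / 0.02) and 100-500 patients, DE is 1.001-1.048 and the error 5.0-5.6%. With no clustering of the exposure, simulated chi-square tests rejected in 4.8-5.5% of null runs. With 20 hospitals of unequal size (coefficient of variation 0.5), the simulated error reached 9.0% for 100-150 patients and 17.9% for 500. The number eligible for question 3 is not given, so no figure is offered for it.

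**Step 2: confounding by hospital.** Step 1 takes hospital levels of exposure and outcome as uncorrelated. Let them correlate at r, with no effect of management within any hospital. The spurious risk difference is about r × √(ICCx × px(1 − px) × ICCy × py(1 − py)) / [px(1 − px)]. Assume exposure 40%, outcome 30%, ICCs 0.3 / 0.075 and 40 hospitals.
- r = 0.3: 0.3 × √(0.3 × 0.24 × 0.075 × 0.21) / 0.24 = 4.2 percentage points. Simulated chi-square tests rejected in about 8% of runs with 125 patients and 18-19% with 500.
- r = 0.5: 7.0 points, with rejection in about 14% and 37-38%.

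**Step 3: which remedy works with few patients per hospital.** Simulations under the null used 20 hospitals and 100-150 patients, with equal and unequal sizes.

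| Method | Rejection at nominal 5% |
|---|---|
| Chi-square ignoring hospital | 5.3-9.0% |
| Cluster-robust, uncorrected | 6.8-8.3% |
| Cluster-robust, variance × H/(H − 1), t with H − 1 df | 4.6-5.8% |
| Random hospital intercept (linear mixed model) | 5.5-6.2% |

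Ordinary logistic regression with hospital dummies behaves badly in small hospitals. With ICCs 0.3 / 0.075, null rejection was about 10-11% at 60 hospitals × 2 patients and 8-8.5% at 40 × 3. A true odds ratio of 2 had a median estimate of about 4.0 and 3.2 respectively.

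**Step 4: proportions.** Here DE = 1 + (m − 1) × ICC, with the practice ICC alone. At 500 patients, the smallest value is 1 + 7.33 × 0.2 = 2.5 and the largest 1 + 24 × 0.4 = 10.6, so the interval is √2.5 = 1.6 to √10.6 = 3.3 times as wide. At 125 patients the factor is 1.1-1.8.

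**Step 5: price of the small-sample correction.** √(H/(H − 1)) × t(0.975, H − 1) / 1.96 gives 1.096, 1.045 and 1.030 for 20, 40 and 60 hospitals.

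**The case against.** The strongest reply is that nothing in the documents shows a wrong analysis. The simple tests may be meant for descriptive tables, and the announced regression may include hospital, since hospital characteristics are collected. That stands. A reader might infer that the plan has decided to ignore hospital, but the documents only fail to say, so this is an omission.

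Clustering by hospital is also inferred. The Background attributes management to the preferences of surgeons, not to hospital policy. If surgeons within one hospital differ, hospital clustering may be weak and the tests near nominal. The 72-hour exposure in question 3 is set patient by patient, which points the same way for variance, though confounding by hospital can remain.

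Much of the plan is counting: questions 1 and 2 and the first half of question 4. The second half of question 4 names no comparator. The higher error figures need a comparison across all 500 patients, for which only the broad research question and the regression sentence give a basis. In the operated subset the midpoint illustration is 5.6%. All of this limits the weight of the point.

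It does not remove it. Question 3 and the overall question are about effects, the section on analysis offers no method for them that handles hospital, and a short addition would settle the matter.

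**Conclusion.** The point holds as an omission that should be corrected, with moderate confidence. The named tests assume independence, and no stated method accounts for hospital in a multicentre study of practice variation.

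Under the assumed inputs, the actual error is about 5-8% with 100-150 patients and 6-16% with 500. It is somewhat higher with unequal hospitals and close to 5% if management is evenly mixed within hospitals. Hospital confounding could matter more than the variance effect, but its size depends on a correlation about which the documents say nothing.

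A reader might go further and infer an error rate near 29%. That needs an exposure fixed entirely by hospital, only 20 hospitals and an outcome ICC of 0.10 (DE = 1 + 24 × 0.10 = 3.4). Nothing in the documents supports treating management as purely a hospital policy.

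**What to change.** - **Outcome comparisons.** State the regression model. For question 3, any outcome comparison under question 4, and the practice-variation comparisons, base inference on that regression with hospital accounted for. Use either a random hospital intercept, or GEE/cluster-robust standard errors with a small-sample correction. The correction can be done by hand: multiply the robust standard error by √(H/(H − 1)) and refer to t with H − 1 degrees of freedom. Uncorrected robust errors were no better overall than ignoring hospital at 20 hospitals. The random intercept was checked only as a linear model, so its performance in a logistic model is not shown here.
- **Within- versus between-hospital effects.** Add the hospital mean of the exposure, or use conditional logistic regression or a linear fixed-effects model. Do not use ordinary logistic regression with hospital dummies when hospitals contribute few patients.
- **Proportions in questions 1 and 4.** Give 95% confidence intervals, accounting for hospital if inference beyond the participating hospitals is intended. If nearly all Dutch hospitals take part, treating them as a random sample is a choice that the plan should state.
- **Simple tests.** Keep them for descriptive tables.

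**Cost.** This needs analysis wording and a hospital code with each exported record; Data handling mentions export but no such code. For the comparisons, the small-sample correction alone widens intervals by 3-10%. For proportions the widening could be 1.6-3.3 times at 500 patients under practice ICCs of 0.2-0.4. In the operated subset, at 100/60 = 1.7 to 150/20 = 7.5 patients per hospital, between-hospital variance estimates may be unstable.

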## Data handling

For our data handling we will use the Castor software, made by Ciwit located in Amsterdam, which has been optimized for medical research according to good clinical practice standards. The questions are predefined by the project steering group. Questions will be tested for clarity and will be relatively easy to fill to ensure a high data density, and lowering the threshold for hospitals to participate. The data can be managed in the Castor program, and exported to statistical software packages for analysis. The patient information will be anonymous and coded with numbers in our database. The decoding key of a patient is only available to the hospitals which put their patient into the system.

## Societal and ethical justification

This is an observational research project, patients included in this research will not undergo any intervention or treatment as part of the research project. Therefore this study is not WMO-compulsory. The patient cannot be identified from the questionnaire, because the patient data does not contain personal information. Within this study, patients will be used as numbers, without using personal relatable information. This is in line with Good clinical practice.

Assuming that this snapshot study will provide information for an improved guideline for management and treatment of ASBO, the relevance for science of society will be noticeable for different kind of stakeholders. Potential stakeholders are clinicians, patients, health insurance companies and patient societies.

